9.3.1.8 Final Study Visit, Day 35 ± 2 days

All subjects will present to their local site on Day 35 ± 2 days. Site will conduct assessments to complete the UPDRS, PGI, CGI, and Epworth Sleepiness Scale, as well as safety assessments. An untimed sample will be collected for PK analysis. The investigator must complete the End of Study eCRF page.

Subjects who have abnormal, clinically significant (CS) findings at the Final Study Visit may be asked, per investigator's discretion, to return to the clinic subsequently to ensure appropriate safety follow-up.

9.3.2 Early Termination

Subjects who discontinue dosing or decide to check out of the study clinic early will be advised to allow the Investigator (or authorized designees) to complete early termination assessments for safety purposes prior to discharge. The reason for discontinuation must be documented in the source document and eCRF.

For all subjects receiving study medication, the investigator must complete the End of Study eCRF page.

9.4 Biological Sample Retention and Destruction

In this study, specimens for genome/gene analysis will be collected as described in Section 9.1.12, Pharmacogenomic Sample Collection. After extraction and purification, the genetic material will be preserved and retained at a biorepository selected by the sponsor for up to but not longer than 15 years or as required by applicable law. The sponsor has put into place a system to protect the subjects' personal information to ensure optimal confidentiality and defined standard processes for sample and data collection, storage, analysis, and destruction.

The sample will be labeled with a unique sample identifier similar to labeling in the main study but using a code that is different from the code attached to the health information and other clinical test results collected in the study. The sample and data are linked to personal health information with code numbers; the samples are stripped of all personal identifying information but a key linking the samples to clinical analysis data exists. This link means that the subject may be identified but only indirectly. The code numbers will be kept secure by or on behalf of the Sponsor.

Subjects who consented and provided a pharmacogenomic sample for DNA and RNA analysis can withdraw their consent and request disposal of a stored sample at any time prior to analysis. The Investigator will notify the sponsor of any subject who has withdrawn consent for the DNA and RNA analysis.

Study No. CVN424-201 Page 46 of 73

Protocol v. 4.0 14 July 2021

9.5 Definitions

9.5.1 PTE

A PTE is defined as any untoward medical occurrence in a clinical investigation subject who has signed the ICF to participate in a study but prior to administration of any study medication; it does not necessarily have to have a causal relationship with study participation.

9.5.2 AE

An AE is defined as any untoward medical occurrence in a clinical investigation subject administered a drug; it does not necessarily have to have a causal relationship with this treatment.

An AE can therefore be any unfavorable and unintended sign (e.g., a CS abnormal laboratory finding), symptom, or disease temporally associated with the use of a drug whether or not it is considered related to the drug.

9.5.3 Additional Points to Consider for PTEs and AEs

An untoward finding generally may:

- Indicate a new diagnosis or unexpected worsening of a pre-existing condition. (Intermittent events for pre-existing conditions underlying disease should not be considered PTEs or AEs)
- Necessitate therapeutic intervention
- Require an invasive diagnostic procedure
- Require discontinuation or a change in dose of study medication or a concomitant medication
- Be considered unfavorable by the investigator for any reason
- PTEs/AEs caused by a study procedure (e.g., a bruise after blood draw) should be recorded as a PTE/AE

Diagnoses vs signs and symptoms:

• Each event should be recorded to represent a single diagnosis. Accompanying signs (including abnormal laboratory values or ECG findings) or symptoms should NOT be recorded as additional AEs. If a diagnosis is unknown, sign(s) or symptom(s) should be recorded appropriately as a PTE(s) or as an AE(s)

Laboratory values and ECG findings:

Changes in laboratory values or ECG parameters are only considered to be PTEs or AEs if they
are judged to be CS (i.e., if some action or intervention is required). A laboratory re-test and/or
continued monitoring of an abnormal value are not considered an intervention. In addition,
repeated or additional noninvasive testing for verification, evaluation or monitoring of an
abnormality is not considered an intervention

Study No. CVN424-201 Page 47 of 73

Protocol v. 4.0 14 July 2021

• If abnormal laboratory values or ECG findings are the result of pathology for which there is an overall diagnosis (e.g., increased creatinine in renal failure), the diagnosis only should be reported appropriately as a PTE or as an AE

Pre-existing conditions:

- Pre-existing conditions (present at the time of signing of the ICF) are considered concurrent medical conditions and should NOT be recorded as PTEs or AEs. Baseline evaluations (e.g., laboratory tests, ECG, X-rays etc.) should NOT be recorded as PTEs unless related to study procedures. However, if the subject experiences a worsening or complication of such a concurrent condition, the worsening or complication should be recorded appropriately as a PTE (worsening or complication occurs before start of study medication) or an AE (worsening or complication occurs after start of study medication). Investigators should ensure that the event term recorded captures the change in the condition (e.g., "worsening of...")
- If a subject has a pre-existing episodic condition (e.g., asthma, epilepsy) any occurrence of an episode should only be captured as a PTE/AE if the episodes become more frequent, serious or severe in nature, that is, investigators should ensure that the AE term recorded captures the change in the condition from Baseline (e.g., "worsening of...")
- If a subject has a degenerative concurrent condition (e.g., cataracts, rheumatoid arthritis), worsening of the condition should only be captured as a PTE/AE if occurring to a greater extent to that which would be expected. Again, investigators should ensure that the AE term recorded captures the change in the condition (e.g., "worsening of...")

Worsening of PTEs or AEs:

- If the subject experiences a worsening or complication of a PTE after starting administration of the study medication, the worsening or complication should be recorded appropriately as an AE. Investigators should ensure that the AE term recorded captures the change in the condition (e.g., "worsening of...")
- If the subject experiences a worsening or complication of an AE after any change in study medication, the worsening or complication should be recorded as a new AE. Investigators should ensure that the AE term recorded captures the change in the condition (e.g., "worsening of...")

Changes in severity of AEs /Serious PTEs:

• If the subject experiences changes in severity of an AE/serious PTE, the event should be captured once with the maximum severity recorded

Preplanned surgeries or procedures:

Preplanned procedures (surgeries or therapies) that were scheduled prior to signing of informed
consent are not considered PTEs or AEs. However, if a preplanned procedure is performed early
(e.g., as an emergency) due to a worsening of the pre-existing condition, the worsening of the
condition should be captured appropriately as a PTE or an AE. Complications resulting from any
planned surgery should be reported as AEs

Study No. CVN424-201 Page 48 of 73

Protocol v. 4.0 14 July 2021

Elective surgeries or procedures:

• Elective procedures performed where there is no change in the subject's medical condition should not be recorded as PTEs or AEs, but should be documented in the subject's source documents. Complications resulting from an elective surgery should be reported as AEs

Overdose:

 Cases of overdose with any medication without manifested side effects are NOT considered PTEs or AEs, but instead will be documented on an Overdose page of the eCRF. Any manifested side effects will be considered PTEs or AEs and will be recorded on the AE page of the eCRF

9.5.4 **SAEs**

An SAE is defined as any untoward medical occurrence that at any dose:

- 1. Results in DEATH.
- 2. Is LIFE THREATENING.
- The term "life threatening" refers to an event in which the subject was at risk of death at the time of the event; it does not refer to an event that hypothetically might have caused death if it were more severe
- 3. Requires inpatient HOSPITALIZATION or prolongation of existing hospitalization.
- 4. Results in persistent or significant DISABILITY/INCAPACITY.
- 5. Leads to a CONGENITAL ANOMALY/BIRTH DEFECT.
- 6. Is an IMPORTANT MEDICAL EVENT that satisfies any of the following:
- May require intervention to prevent items 1 through 5 above
- May expose the subject to danger, even though the event is not immediately life threatening or fatal or does not result in hospitalization
- Includes any event or synonym described in the Medically Significant AE List (Table 7)

Study No. CVN424-201 Page 49 of 73

Protocol v. 4.0 14 July 2021

Table 7 Medically Significant AE List

Term							
Acute respiratory failure/acute respiratory distress syndrome	Hepatic necrosis						
Torsade de pointes / ventricular fibrillation / ventricular	Acute liver failure						
tachycardia	Anaphylactic shock						
Malignant hypertension	Acute renal failure						
Convulsive seizure	Pulmonary hypertension						
Agranulocytosis	Pulmonary fibrosis						
Aplastic anemia	Confirmed or suspected endotoxin shock						
Toxic epidermal necrolysis/Stevens-Johnson syndrome	Confirmed or suspected transmission of infectious agent by a medicinal product						
	Neuroleptic malignant syndrome / malignant hyperthermia						
	Spontaneous abortion / stillbirth and fetal death						

PTEs that fulfill 1 or more of the serious criteria above are also to be considered SAEs and should be reported and followed up in the same manner (see Sections 9.6.2 and 9.7).

9.5.5 Severity of PTEs and AEs

The different categories of intensity (severity) are characterized as follows:

Mild: The event is transient and easily tolerated by the subject.

Moderate: The event causes the subject discomfort and interrupts the subject's usual activities. Severe: The event causes considerable interference with the subject's usual activities.

9.5.6 Causality of AEs

The relationship of each AE to study medication(s) will be assessed using the following categories:

Related: An AE that follows a reasonable temporal sequence from administration of a drug (including the

course after withdrawal of the drug), or for which possible involvement of the drug can be argued, although factors other than the drug, such as underlying diseases, complications,

concomitant drugs and concurrent treatments, may also be responsible.

Not Related: An AE that does not follow a reasonable temporal sequence from administration of a drug

and/or that can reasonably be explained by other factors, such as underlying diseases,

complications, concomitant drugs and concurrent treatments.

9.5.7 Relationship to Study Procedures

Relationship (causality) to study procedures should be determined for all PTEs and AEs.

The relationship should be assessed as Related if the investigator considers that there is reasonable possibility that an event is due to a study procedure. Otherwise, the relationship should be assessed as Not Related.

Study No. CVN424-201 Page 50 of 73

Protocol v. 4.0 14 July 2021

9.5.8 Start Date

The start date of the AE/PTE is the date that the first signs/symptoms were noted by the subject and/or physician.

9.5.9 Stop Date

The stop date of the AE/serious PTE is the date at which the subject recovered, the event resolved but with sequelae or the subject died.

9.5.10 Frequency

Episodic AEs/serious PTE (e.g., vomiting) or those which occur repeatedly over a period of consecutive days are intermittent. All other events are continuous.

9.5.11 Action Concerning Study Medication

- Drug withdrawn a study medication is stopped due to the particular AE
- Dose not changed the particular AE did not require stopping a study medication
- Unknown only to be used if it has not been possible to determine what action has been taken
- Not Applicable a study medication was stopped for a reason other than the particular AE e.g., the study has been terminated, the subject died, dosing with study medication was already stopped before the onset of the AE

9.5.12 Outcome

- Recovered/Resolved Subject returned to first assessment status with respect to the AE/serious PTE
- Recovering/Resolving the intensity is lowered by one or more stages: the diagnosis or signs/symptoms has almost disappeared; the abnormal laboratory value improved, but has not returned to the normal range or to baseline; the subject died from a cause other than the particular AE/serious PTE with the condition remaining "recovering/resolving"
- Not recovered/not resolved there is no change in the diagnosis, signs or symptoms; the intensity of the diagnosis, signs/ symptoms or laboratory value on the last day of the observed study period has got worse than when it started; is an irreversible congenital anomaly; the subject died from another cause with the particular AE/serious PTE state remaining "Not recovered/not resolved"
- Resolved with sequelae the subject recovered from an acute AE/serious PTE but was left with permanent/significant impairment (e.g., recovered from a cardiovascular accident but with some persisting paresis
- Fatal the AEs/PTEs which are considered as the cause of death

Study No. CVN424-201 Page 51 of 73

Protocol v. 4.0 14 July 2021

• Unknown – the course of the AE/serious PTE cannot be followed up due to hospital change or residence change at the end of the subject's participation in the study

9.6 Procedures

9.6.1 Collection and Reporting of AEs

9.6.1.1 PTE and AE Collection Period

Collection of PTEs will commence from the time the subject signs the informed consent to participate in the study and continue until the subject is first administered study medication Day 1 or until screen failure. For subjects who discontinue prior to study medication administration, PTEs are collected until the subject discontinues study participation.

Collection of AEs will commence from the time that the subject is first administered study medication Day 1. Collection of AEs will continue until 14 days following last dose. Ascertainment of AEs with onset or worsening after the Final Study Visit on Day 35 and within 14 days of last dose will rely on spontaneous reporting by the subject or caregiver.

9.6.1.2 PTE and AE Reporting

At each study visit, the investigator or designee will assess whether any subjective AEs have occurred. A neutral question, such as "How have you been feeling since your last visit?" may be asked. Subjects may report AEs occurring at any other time during the study. Subjects experiencing a serious PTE must be monitored until the symptoms subside and any clinically relevant changes in laboratory values have returned to baseline or there is a satisfactory explanation for the change. Non-serious PTEs, related or unrelated to the study procedure, need not to be followed-up for the purposes of the protocol.

All subjects experiencing AEs, whether considered associated with the use of the study medication or not, must be monitored until the symptoms subside and any clinically relevant changes in laboratory values have returned to baseline or until there is a satisfactory explanation for the changes observed. All PTEs and AEs will be documented in the PTE/AE page of the eCRF, whether or not the investigator concludes that the event is related to the drug treatment. The following information will be documented for each event:

- 1. Event term.
- 2. Start and stop date and time.
- 3. Frequency.
- 4. Severity.
- 5. Investigator's opinion of the causal relationship between the event and administration of study medication(s) (related or not related) (not completed for PTEs).
- 6. Investigator's opinion of the causal relationship to study procedure(s), including the details of the suspected procedure.

Study No. CVN424-201 Page 52 of 73

Protocol v. 4.0 14 July 2021

- 7. Action concerning study medication (not applicable for PTEs).
- 8. Outcome of event.
- 9. Seriousness.

9.6.2 Collection and Reporting of SAEs

When an SAE occurs through the AE collection period it should be reported according to the following procedure:

An SAE form must be completed, in English, and signed by the investigator immediately or within 24 h of first onset or notification of the event. The information should be completed as fully as possible but contain, at a minimum:

- A short description of the event and the reason why the event is categorized as serious
- Subject identification number
- Investigator's name
- Name of the study medication(s)
- Causality assessment

The SAE form should be transmitted within 24 h to the attention of the contact listed in Section 1.0.

Any SAE spontaneously reported to the investigator following the AE collection period should be reported to the sponsor if considered related to study participation.

Reporting of Serious PTEs will follow the procedure described for SAEs.

9.6.3 Reporting of Abnormal LFT

If a subject is noted to have ALT or AST elevated >3 ×ULN on 2 consecutive occasions, the abnormality should be recorded as an AE.

If a subject is noted to have ALT or AST >3 ×ULN and total bilirubin >2 ×ULN for which an alternative etiology has not been identified, the event should be recorded as an SAE and reported as per Section 9.6.2. The investigator must contact the Medical Monitor for discussion of the relevant subject details and possible alternative etiologies, such as acute viral hepatitis A or B or other acute liver disease or medical history/concurrent medical conditions. Follow-up laboratory tests as described in Section 9.1.8 must also be performed.

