- One or more subjects receiving CVN424 experience ALT and/or AST elevations >3 ×ULN in the presence of a total bilirubin increase >2 ×ULN or an international normalized ratio (INR) >1.5 without findings of cholestasis or other alternate etiology to explain the elevations (i.e., "Hy's Law cases").
- Two or more subjects receiving CVN424 experience ALT and/or AST elevations >3 ×ULN with the appearance of fatigue, nausea, vomiting, right upper quadrant pain or tenderness, fever, rash and/or eosinophilia (>5%).

Primary Objective:

To assess the safety and tolerability of CVN424 when administered as daily oral doses for 28 days, adjunctive to levodopa, in subjects with Parkinson's disease and motor fluctuations.

Study No. CVN424-201 Page 11 of 73

Protocol v. 4.0 14 July 2021

Secondary Objectives:

- To assess potential efficacy of CVN424 adjunctive to levodopa in alleviating symptoms of PD
- To assess CVN424 multiple-dose PK in blood of PD subjects

Exploratory Objectives:

• To explore possible serum/plasma, DNA and/or RNA markers (e.g., drug metabolic enzyme and transporter polymorphisms) that may contribute to variability in CVN424 PK, safety or efficacy

Subject Population:

Male and female subjects, ages 30 to 80 years old, with idiopathic Parkinson's disease and motor fluctuations on stable doses of levodopa

Target Number of Subjects:	Number of Sites:
45 subjects per arm (total n=135 subjects)	Approximately 30 in the United States of America
Dose Level(s):	Route of Administration:
Planned dose levels are placebo, 50 mg, and 150 mg CVN424. Study drug dispensed as CVN424 suspension (or matching placebo) in amber colored bottles suitable for self-administered dosing.	Oral
Duration of Treatment:	Period of Evaluation:
Daily oral doses for 28 days.	Screening Period: up to 28 days
	Treatment Period: 28 days
	Follow-up Period: approximately 7 days
	Total Duration: Approximately 9 weeks

Main Criteria for Inclusion:

- 1. Male or female adult who is 30 to 80 years of age inclusive at study entry.
- 2. Has idiopathic Parkinson's disease, Hoehn and Yahr stages 2-4, and is on a stable dosage of levodopa. (Stable is defined as a dosage unchanged in the 30 days prior to randomization and, in the opinion of the investigator, able to continue the current regimen throughout the month-long study without undue inconvenience or harm.)

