6.3 Premature Termination or Suspension of Study or Investigational Site

6.3.1 Criteria for Premature Termination or Suspension of the Study

The study will be completed as planned unless new information or other evaluation regarding the safety of the study medication indicates an adverse change in the risk profile for the compound, such that Sponsor or an Institutional Review Board (IRB) or Ethics Committee considers the risk is no longer acceptable for subjects participating in the study.

If any of the following occur, the Medical Monitor and Sponsor's Responsible Medical Officer will review the relevant data, including unblinded data if deemed necessary, and decide whether it is safe to suspend dosing or continue dosing at either the planned or alternative dose levels or decides to prematurely terminate the study:

- 1. Four or more subjects receiving CVN424 experience the same type of serious or Medically Significant event deemed related to study drug.
- 2. Three or more subjects receiving CVN424 experience alanine aminotransferase (ALT) and/or aspartate aminotransferase (AST) elevations >5 × upper limit of normal (ULN) in the absence of a concomitant bilirubin increase.
- 3. One or more subjects receiving CVN424 experience ALT and/or AST elevations >3 ×ULN in the presence of a total bilirubin increase >2 ×ULN or an international normalized ratio (INR) >1.5 without findings of cholestasis or other alternate etiology to explain the elevations (i.e., "Hy's Law cases").
- 4. Two or more subjects receiving CVN424 experience ALT and/or AST elevations >3 ×ULN with the appearance of fatigue, nausea, vomiting, right upper quadrant pain or tenderness, fever, rash and/or eosinophilia (>5%).

In addition, the study may be terminated at the discretion of the Sponsor.

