7.5 Criteria for Discontinuation or Withdrawal of a Subject

The following represent criteria that require discontinuation of study drug and/or withdrawal from the study. The primary reason for discontinuation or withdrawal of the subject from the study or study medication should be recorded in the electronic case report form (eCRF). For screen failure subjects, refer to Section 9.1.15.

- 1. The subject has experienced a pretreatment event (PTE) or AE that requires early termination because continued participation imposes an unacceptable risk to the subject's health or the subject is unwilling to continue because of the PTE or AE.
- 2. Liver Function Test (LFT) abnormalities meeting prespecified criteria.

Study medication should be discontinued immediately with appropriate clinical follow-up (including repeat laboratory tests, until a subject's laboratory profile has returned to normal/baseline status, see Section 9.1.8), if the following circumstances occur at any time during study medication treatment:

Study No. CVN424-201 Page 29 of 73

Protocol v. 4.0 14 July 2021

- ALT or AST >8 × ULN, or
- ALT or AST >5 × ULN and persists for more than 2 weeks, or
- ALT or AST >3 × ULN in conjunction with elevated total bilirubin >2 × ULN or INR >1.5, or
- ALT or AST >3 × ULN with appearance of fatigue, nausea, vomiting, right upper quadrant pain or tenderness, fever, rash and/or eosinophilia (>5%).
- 3. Lost to follow-up. The subject did not return to the clinic and attempts to contact the subject were unsuccessful. Attempts to contact the subject must be documented.
- 4. Voluntary withdrawal. The subject (or subject's legally acceptable representative) wishes to withdraw from the study. The reason for withdrawal, if provided, should be recorded in the eCRF.

Note: Attempts should be made to determine the underlying reason for the withdrawal and, where possible, the primary underlying reason should be recorded (e.g., withdrawal due to an AE; withdrawal due to relocation).

5. The sponsor, IRB, IEC, or regulatory agency terminates the study.

Additionally, the Investigator should consider discontinuation of study drug and/or withdrawal from the study for subjects with a major protocol deviation, including violation of protocol entry criteria, such that continuation on study poses an unacceptable risk to the subject's health or to the study's scientific objectives.

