All CS laboratory abnormalities must be recorded as a PTE/AE in the subject's source documents and on the appropriate eCRF. A CS laboratory abnormality that has been verified by retesting will be followed until the abnormality returns to an acceptable level or a satisfactory explanation has been obtained.

⁽a) Serum hCG pregnancy test will be done at Screening in women subjects.

⁽b) FSH level will be obtained for female subjects at Screening if they are postmenopausal (i.e., last regular menstrual cycle >2 years) and not surgically sterile. The result must be >40 IU/L for the subject to be enrolled.

Study No. CVN424-201 Page 37 of 73

Protocol v. 4.0 14 July 2021

If subjects experience ALT or AST >3 ×ULN, follow-up laboratory tests (at a minimum, serum alkaline phosphatase, ALT, AST, total bilirubin, GGT, and INR) should be performed within a maximum of 7 days and preferably within 48 to 72 h after the abnormality was found.

(Please refer to Section 7.4 for discontinuation criteria, and Section 9.6.3 for the appropriate guidance on Reporting of Abnormal LFT in relation to ALT or AST >3 ×ULN in conjunction with total bilirubin >2 ×ULN).

If the ALT or AST remains elevated >3 ×ULN on these 2 consecutive occasions, the investigator must contact the Medical Monitor for consideration of additional testing, close monitoring, possible discontinuation of study medication, discussion of the relevant subject details and possible alternative etiologies. The abnormality should be recorded as an AE (please refer to Section 9.6.3 Reporting of Abnormal LFT for reporting requirements).

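### ALT/AST >3 ×ULN with INR >1.5 triggers study review and an immediate drug stop, but section 9.6.3 gives automatic SAE status and Medical Monitor contact on the first raised sample only to the bilirubin limb

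*Combined protocol and SAP*

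**What the plan says.** Two rules treat raised bilirubin and raised INR as alternatives.

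- **Study-level review.** Section 6.3.1, rule 3, is met by one subject on CVN424 with ALT or AST >3 ×ULN "in the presence of a total bilirubin increase >2 ×ULN or an international normalized ratio (INR) >1.5", provided cholestasis or another cause does not explain it. The synopsis repeats the rule ("total bilirubin increase >2 ×ULN or an international normalized ratio (INR) >1.5"). When it is met, the Medical Monitor and the sponsor's Responsible Medical Officer are to "review the relevant data, including unblinded data if deemed necessary, and decide whether it is safe to suspend dosing or continue dosing".
- **Subject-level stop.** Section 7.5 requires immediate discontinuation of study drug for "ALT or AST >3 × ULN in conjunction with elevated total bilirubin >2 × ULN or INR >1.5". It carries no exclusion for other causes.

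The reporting text names bilirubin only.

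- **Section 9.6.3** requires an SAE record, reporting under 9.6.2 and contact with the Medical Monitor for "ALT or AST >3 ×ULN and total bilirubin >2 ×ULN for which an alternative etiology has not been identified". Under 9.6.2 the SAE form is due "immediately or within 24 h of first onset or notification of the event".
- **Section 9.1.8** points to 9.6.3 "in relation to ALT or AST >3 ×ULN in conjunction with total bilirubin >2 ×ULN". The same sentence sends the reader to Section 7.4 for discontinuation criteria; 7.4 is Diet and Fluid Control, and the criteria are in 7.5.

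A separate duty in 9.1.8 does not depend on bilirubin or INR. Any ALT or AST >3 ×ULN must be retested within 7 days, preferably within 48 to 72 h. "If the ALT or AST remains elevated >3 ×ULN on these 2 consecutive occasions, the investigator must contact the Medical Monitor".

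**The concern.** Rule 3 is the only liver rule in 6.3.1 that a single case can meet; rules 2 and 4 need three and two subjects. It counts subjects receiving CVN424, so a blinded investigator cannot tell whether it has been met. Only the Medical Monitor and the Responsible Medical Officer can apply it, and sections 6.1.1 and 10.0 provide no safety committee behind them. The rule works only if the site tells them promptly.

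For the bilirubin limb, 9.6.3 makes that notice automatic. For the INR limb it does not, although the protocol puts both limbs under the same Hy's Law label. The documents give no reason for leaving INR out. It does not look deliberate: prothrombin time/INR is in the routine panel (Table 4) and in the minimum retest set in 9.1.8. At stake is how soon the sponsor looks at a possible liver signal while other subjects continue dosing.

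**Working it through.** The protocol states no figure to reproduce here. The check applies each rule to two constructed subjects. Both are on CVN424, with no symptoms, no cholestasis and no other identified cause, and each is seen on a first raised sample.

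- Case A (INR limb): ALT 4 ×ULN, bilirubin 1.5 ×ULN, INR 1.7. ALT 4 > 3 is met; bilirubin 1.5 > 2 is not met; INR 1.7 > 1.5 is met.
- Case B (bilirubin limb): ALT 4 ×ULN, bilirubin 2.5 ×ULN, INR 1.0. ALT 4 > 3 is met; bilirubin 2.5 > 2 is met; INR 1.0 > 1.5 is not met.

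| Rule | Case A | Case B |
|---|---|---|
| 6.3.1 rule 3: study-level review on one case | met | met |
| 7.5: immediate drug stop | met | met |
| 9.6.3: automatic SAE, 24 h form under 9.6.2 | not met | met |
| 9.6.3: Medical Monitor contact on the first raised sample | not met | met |
| 9.1.8: Medical Monitor contact if ALT or AST is still >3 ×ULN at retest | conditional | conditional |

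The rest of the protocol does apply to Case A:

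1. Section 9.5.3 treats a laboratory change as an AE when it is clinically significant, meaning that some action is needed. The 7.5 drug stop is such an action.
2. Section 9.1.8 requires every clinically significant laboratory abnormality to be recorded. The first raised sample is therefore already a recordable AE, without waiting for the second occasion named in 9.6.3.
3. Section 9.6.1.2 requires seriousness and the action taken with study drug to be documented for that AE.
4. Section 9.5.4 lets the investigator class it as an important medical event, which would start the 24 h clock. Acute liver failure, if diagnosed, is a listed term in Table 7.
5. If none of these leads to an SAE report, the next mandatory contact is the one in 9.1.8, and only if the retest is still >3 ×ULN. If the retest has fallen to 3 ×ULN or below, no liver-specific rule requires contact.

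If INR first exceeds 1.5 at the retest while ALT or AST is still >3 ×ULN, 9.1.8 already requires contact. The gap is thus confined to the INR pattern on a first raised sample.

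**The case against.** The strongest reply is that the reporting routes for an INR case are better than 9.6.3 alone suggests. A reader might infer that such a case goes unreported, or is recorded only after two raised samples. The documents do not support that, for the reasons in steps 1 to 4 of the working. An investigator who sees a pattern the protocol itself labels Hy's Law has a clear basis for calling it serious. What is missing is automatic SAE status and the matching first-finding contact, not every route. That part of the reply stands. Even so, the important-medical-event route rests on judgement and the Table 7 route on a diagnosis. The eCRF entries, the laboratory data transfer in 9.1.8 and the standing sponsor review in 6.1.1 carry no stated deadline.

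A reader might also subtract the 24 h SAE clock from the retest interval and quote a delay. The text does not allow it. The 24 h clock governs the SAE form, the Medical Monitor contact in 9.6.3 has no stated deadline for either limb, and the preferred 48 to 72 h is not a fixed time, so an earlier retest complies.

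Rules 2 and 4 in 6.3.1, and the >8 ×ULN and symptom stops in 7.5, also lack automatic SAE status. The protocol does not tie every trigger to SAE reporting, and that is a fair point. Rule 3 differs because one case is enough and 9.6.3 already covers half of it.

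Last, anticoagulants are not prohibited in Table 2. An anticoagulant explains a raised INR but not a raised ALT, so the existing alternative-cause qualifier may not screen out these cases. That objection stands, and the fix has to deal with it.

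**Conclusion.** The mismatch is real and should be corrected, but its reach is limited. For an INR-limb case on a first raised sample, a site following 9.6.3 literally is not automatically required to notify promptly the only people who can apply a one-case trigger. Notice rests on the investigator's judgement of seriousness, or on a retest due within at most 7 days that is still >3 ×ULN.

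A reader might go further and infer that the affected subject stays at risk or that a mandatory halt would be missed. Neither follows: 7.5 takes the subject off drug at once, and rule 3 prompts a review whose outcome may be to continue. The benefit is prompter sponsor review for the other subjects. No endpoint or analysis is affected.

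This assumes that the omission of INR in 9.6.3 is unintended, which fits the rest of the text but is not stated. The pattern is presumably rare; the documents give no basis for a rate.

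**What to change.** Leave all thresholds as they are.

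1. In 9.6.3, widen the SAE and Medical Monitor condition to *total bilirubin >2 ×ULN or INR >1.5*. Keep the alternative-etiology qualifier, and state that an INR rise explained by anticoagulant use does not by itself meet the INR limb.
2. Make the same addition to the pointer in 9.1.8.
3. In 9.1.8, correct the reference for discontinuation criteria from Section 7.4 to Section 7.5. This is editorial.

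The cost is three small wording changes and a few more SAE reports and calls. No new test is needed, since INR is already measured.
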